procedure with will equate study conditions based upon 1) age discrepancy between partners, 2) relationship length, and 3)

race and ethnicity using Qualtrics.

DATA COLLECTION: Participants have the options to first complete a CASI at home

before their BL appointment (or during BL if they have not done so beforehand). All other aspects of data collection occur at Hunter College. A second CASI survey will also be administered at the BL appointment. Time line follow back interviews to assess drug use, sexual behavior and PrEP adherence (where applicable) will at all assessments. Drug screening and PrEP adherence will be accomplished by obtaining fingernail samples from participants at all assessments. Blood will be collected for

testing PrEP medication adherence. STI testing will be

accomplished by collecting urine and rectal samples at BL, 6m, and 12m. HIV testing will be conducted at BL, 6m, and 12m.

Post-COVID: Participants receive a CASI link via email and an athome STI and HIV testing kit, a dried blood spot (DBS) collection kit for PrEP adherence, and a fingernail collection kit for drug screening (via regular mail) prior to assessment appointments.

All other aspects of data collection occur remotely via HIPAA-compliant Zoom.

OBJECTIVES:

- 1) Evaluate the efficacy of PARTNER in regards to three primary outcomes: 1) PrEP uptake and adherence 2) sexual transmission risk behavior and 3) drug use.
- 2) Identify individual and relationship factors which moderate/mediate intervention efforts.
- 3) Gather ideographic data to inform a future effectivenessimplementation study.
- 4) Validate the use of fingernail assays as a biological marker for PrEP adherence.

STUDY DESIGN

[figure not shown]
[figure not shown]

Figure 3. Participation timeline

- ^a To detect drug use for all participants and PrEP adherence for those on PrEP.
- ^b Gathered only for those on PrEP

STUDY TIMELINE

STUDY POPLUATION

Inclusion and Exclusion Criteria:

Participants who express interest in PARTNER must demonstrate the following inclusion criteria to be enrolled in the study:

- 18 29 years old; or 30-34 with a partner who is 18-29 (inclusive)
- Have a main partner who is another male for 1 month or longer
 - Main partner must be 18 years old or older
- Be HIV negative (as confirmed by rapid test)
- Have used drugs in the past 30 days
- Have engaged in TRB in the past 30 days

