Qualtrics, a secure online survey platform which can be accessed from computers on site, is used to administer survey measures during in-person appointments. Qualtrics is sufficiently flexible to permit the use of a wide range of question and response types.

Qualitative interviews will be recorded, transcribed, and de-identified.

MEASURES

CASI Measures

	Construct	Measure
Screening	Demographics	NHBS demographics inventory ¹⁰⁷
information	Sexual HIV transmission risk	Self-Reported Sexual Behavior
	PrEP uptake and related attitudes	PrEP uptake questionnaire ^{15,68}
	Problematic drug use	Drug Abuse Screening Test – 10 ¹⁰⁸
	Alcohol and Drug Use Behavior	NHBS Substance Use History Inventory ¹⁰⁷
	Partner health behavior	Partner health behavior survey
IMB factors	Knowledge: Drug use	Drug use knowledge questionnaire
	Knowledge: HIV infection (including condom and PrEP supplement)	Brief HIV knowledge questionnaire 109
	Motivation: Drug use	Decisional Balance - Club Drugs ¹¹⁰
	Motivation: Condom use	Decisional Balance - Unsafe Sex ¹¹⁰
	Motivation: PrEP	Decisional Balance - PrEP
	Behavioral Skill: Drug use	Drug Taking Confidence Questionnaire ¹¹¹
	Behavioral Skill: Condom use	Condom use self-efficacy scale ¹¹²
	Behavioral Skill: PrEP	Adapted Adherence Self-Efficacy Scale ¹
Individual	Condom attitudes/beliefs	Adapted condom attitudes scale ³²
functioning	Anxiety and Depression	Brief Symptom Inventory ¹¹⁴ (subscales)
	Experiences of stigma	Everyday discrimination ¹¹⁵
	Intimate Partner Violence (IPV)	IPV among gay and bisexual men 116
	Problematic alcohol use	Alcohol Use Disorders Identification Tes (AUDIT) ¹¹⁷
	Self-reported STI and HIV	
	-	

	testing history; PrEP; and ART	
Relationship functioning	Relationship satisfaction, cohesion, consensus & affectional expression	Dyadic adjustment scale ¹¹⁸
	Interpersonal	Interpersonal Communication
	Communication Skills	Competence Scale ¹¹⁹
	Partner communication strategies	Communication patterns questionnaire ¹²⁰
	G	Sexual communication ¹²¹
	Couples HIV Coping	Perceived severity of HIV infection ¹²² Preferences for sexual health outcomes ¹²²
		Couple efficacy to reduce HIV threat 122
	Stigma directed at the relationship	Relationship marginalization ¹²³
	Relationship Control & Dominance	Sexual Relationship Power Scale (SRPS) ¹²⁴
	Attitudes about Sexual Agreements	Sexual Agreement Investment Scale (SAIS) ¹⁰⁰

Primary outcomes

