Drug use. During TLFB interviews, participants indicated whether they used any of 10 different drug types. Responses produced two count variables indicating the number of days participants used cannabis and the number of days they reported the use of any illicit drugs, including: cocaine, crack, methamphetamine, ecstasy, ketamine, GHB, and psychedelics. Self-reported drug use was corroborated by fingernail assay. See supplemental material for details.

Current PrEP uptake was assessed using a single survey item, "Have you ever been prescribed PrEP (HIV pre-exposure prophylaxis)?" Participants taking PrEP reported days they missed their PrEP on the TLFB interview. Responses were used to create a dichotomous variable indicating whether or not participants took PrEP on at least 57% of days (corresponding to at least 4 days out of 7 on average). Self-reported PrEP adherence was corroborated with DBS results. See supplemental material for details.

Sexual HIV TRB. During TLFB interviews, participants indicated days they had (insertive or receptive) anal sex with any casual partners and whether a condom was used. Responses were aggregated to create a variable indicating the number of times the participant had CAS with a casual partner. If participants were prescribed PrEP and reported missing 13 doses or fewer, they were assigned a value of 0, reflecting that the use of PrEP on at least 4 of 7 days is sufficient to achieve reductions in HIV TRB (28). Self-reported CAS with casual partners was corroborated by bacterial STI diagnosis. See supplemental material for details.

Putative moderators

Relationship satisfaction was assessed using the approximation to ideal subscale of Kurdek's (29, 30) Multiple Determinants of Relationship Commitment Inventory (MDRCI). The subscale consists of 4 items (e.g., "My current relationship comes close to matching what I would consider to be my ideal relationship"). Response options ranged from 1 (strongly disagree) to 5 (strongly agree). Total score reliability was good (Cronbach's $\alpha = .848$).

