Communication skills. Self-disclosure, social anxiety, assertiveness, and empathy subscales of the Interpersonal Communication Competence Scale (31) assessed aspects of communication skills. Each subscale was assessed by 3 statements (e.g., "I can put myself in others' shoes" and "It's difficult to find the right words to express myself"). Participants evaluated each statement using a 5-point scale Likert-type scale ranging from 0 ("Almost never") to 4 ("Almost always"). Total score reliability was good (Cronbach's $\alpha = .787$).

Quantitative Analysis Plan

The primary hypotheses are that SMM receiving the PARTNER intervention will be more likely to initiate and/or be adherent to PrEP throughout the follow up period. As a result, it is hypothesized they will have a lower probability of TRB. In addition, it is hypothesized that the PARTNER intervention will be associated with lower levels of drug use (number of use instances) compared to the education condition.

Corroboration of self-reported behavior with biomarkers

Self-reported drug use was corroborated by fingernail assays. At baseline and all follow-ups, at least 80% of participants who tested positive for cannabis indicated at least one instance of cannabis use. In addition, at least 60% of those who did not test positive for cannabis on fingernail assays indicated they used cannabis at least once. At baseline, and all follow-ups, at least 55% of those who tested nail positive for cocaine, crack, or amphetamine use reported at least one instance of illicit drug use. In addition, 12% of those who did not test positive for illicit drug use on nail samples self-reported the use of at least one drug.

Self-reported PrEP adherence was corroborated with DBS results. At baseline and all follow-up time points, no fewer than 69% of participants who reported taking their PrEP on 57% of days or more had a DBS test result of 700 units of TFV-DP per DBS punch or greater at all follow-up time points. One participant at baseline and another at the 3month follow-up reported missing more than 57% of their PrEP but produced a DBS result of 700 units of TFV-DP per DBS punch or more.

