Self-reported CAS with casual partners was corroborated by bacterial STI diagnosis. Participants were indicated as having a bacterial STI if they received a positive result for rectal or urethral gonorrhea or chlamydia at baseline, 6, or 12-month follow-up or if they self-reported receiving a diagnosis in the past 3 months at any assessment point. At baseline, 30.5% of those who

reported CAS with a casual partner had a bacterial STI compared to 7.7% of those who did not. Similarly, 44.2% of participants who reported having CAS with a casual partner at either the 3 or 6-month follow-up had a bacterial STI, compared to 23.9% of those who did not. Finally, 39% of those who reported having CAS with a casual partner at the 9 or 12-month follow-up had a bacterial STI compared to 9.5% of those who did not.

Detailed analytic plan

A series of bivariate analyses ($\chi 2$ tests of independence and independent samples t-tests) conducted in SPSS (version 29) evaluated the success of randomization and the presence of differential attrition. The generalized linear model function in SPSS was used to evaluate between-condition differences in baseline frequency of primary outcomes with count distributions (cannabis use days, other illicit drug use days, sexual HIV TRB) and baseline odds of PrEP uptake (a dichotomous variable).

Outcome analyses were conducted using piece-wise latent growth curve (LGC) models following procedures outlined by Chou et al. Growth trajectories over time following the delivery of an intervention may be characterized by a large initial response followed by a more sustained trajectory with a less dramatic slope. Piece-wise LGC models quantify this kind of trajectory using two slopes. Slope 1 quantifies the change from baseline to the immediate post-test (3-month follow-up). Meanwhile, Slope 2 quantifies the trajectory over the post-intervention follow-up period.

Two models were calculated for each outcome. Model 1 included the main effect of treatment on growth factors. Model 2 added the main effects of moderators (communication skills and relationship quality) as well as the interaction terms between these moderators and the main effect of treatment.

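### The STI check on self-reported casual CAS mixes laboratory results with self-reported diagnoses, and its biological share is not shown

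*Combined protocol and SAP*

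**What the plan says.** In the Quantitative Analysis Plan, under "Corroboration of self-reported behavior with biomarkers", the plan states: "Self-reported CAS with casual partners was corroborated by bacterial STI diagnosis". The same statement appears under Primary outcomes, in the definition of sexual HIV TRB, with a pointer to supplemental material.

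The STI indicator has two limbs joined by an 'or'. The first is a "positive result for rectal or urethral gonorrhea or chlamydia at baseline, 6, or 12-month follow-up". The second reads "or if they self-reported receiving a diagnosis in the past 3 months at any assessment point".

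The abstract says STI testing is "accomplished by collecting urine and rectal samples at BL, 6m, and 12m", and the table under Schedule of Assessments agrees. No STI specimen is scheduled at 3 or 9 months.

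The CAS report itself comes from the timeline follow-back: "During TLFB interviews, participants indicated days they had (insertive or receptive) anal sex with any casual partners and whether a condom was used". The source of the self-reported diagnosis is not named. The CASI measures table has a row beginning "Self-reported STI and HIV", which is the likely source.

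Results are given for the composite only. At baseline, 30.5% of those who "reported CAS with a casual partner had a bacterial STI compared to 7.7% of those who did not". The later figures are 44.2% vs 23.9% for months 3 and 6 together, and 39% vs 9.5% for months 9 and 12 together. No counts, denominators, laboratory-only rates or rates by arm are given.

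**The concern.** A biomarker check on a self-reported outcome is useful because its errors should not depend on what the participant is willing to say. Adding a self-reported diagnosis to the reference weakens that. A man who withholds casual CAS may also withhold a diagnosis, and the check then counts concealment as agreement. A man who discloses one may more readily disclose the other. Both patterns push the association up without any biological link.

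The STI check differs here from its neighbours. In the same section, drug use is compared with fingernail assays and PrEP adherence with dried blood spots, and both references are laboratory results alone.

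At stake is how far the phrase about corroboration can be relied on for a self-reported primary outcome. One arm receives motivational interviewing aimed at this behaviour, so reporting that differs by arm is an obvious threat. The pooled composite rates do not address it.

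**Working it through.** **Inputs.** The three pairs of composite rates come from the corroboration section. Write *a* for the rate among men who reported casual CAS and *b* for the rate among those who did not. The share of positives that rest on self-report only, *s*, is not in the documents. I vary it as an assumption from 0% to 75%. I read the indicator as scored within each reported period. Without counts, the stated percentages cannot be reproduced, so they are taken as given.

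**Step 1: which visits can supply a laboratory positive.**

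| Reported period | Laboratory test | Visit with self-report only |
|---|---|---|
| Baseline | baseline | none |
| 3/6 months | 6 months | 3 months |
| 9/12 months | 12 months | 9 months |

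Every period contains one laboratory test. In the two follow-up periods, a positive first recorded at the 3- or 9-month visit can only be self-reported.

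**Step 2: the composite contrast.** OR = [a/(1−a)] / [b/(1−b)].

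- Baseline: (0.305/0.695) / (0.077/0.923) = 5.26
- 3/6 months: (0.442/0.558) / (0.239/0.761) = 2.52
- 9/12 months: (0.390/0.610) / (0.095/0.905) = 6.09

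**Step 3: break-even share, least favourable case.** Suppose self-report-only positives occur only among CAS reporters. The laboratory rate among them is then a(1−s), and it equals *b* when s = (a−b)/a.

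- Baseline: 0.228/0.305 = 74.8%
- 3/6 months: 0.203/0.442 = 45.9%
- 9/12 months: 0.295/0.390 = 75.6%

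**Step 4: laboratory-only OR over the assumed range of s.**

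| Period | Where s applies | s = 0% | 25% | 50% | 75% |
|---|---|---|---|---|---|
| Baseline | CAS reporters only | 5.26 | 3.56 | 2.16 | 0.99 |
| Baseline | both groups equally | 5.26 | 4.84 | 4.49 | 4.21 |
| 3/6 months | CAS reporters only | 2.52 | 1.58 | 0.90 | 0.40 |
| 3/6 months | both groups equally | 2.52 | 2.27 | 2.09 | 1.95 |
| 9/12 months | CAS reporters only | 6.09 | 3.94 | 2.31 | 1.03 |
| 9/12 months | both groups equally | 6.09 | 5.39 | 4.86 | 4.44 |

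The answer depends on how self-report-only positives divide between the groups, and that is the quantity not reported.

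**Step 5: is a sizeable self-report share plausible?** The Power analyses section planned on a positive STI test in 7% to 13% of the education condition. The composite at 3/6 months is 23.9% even among men who reported no casual CAS. This proves nothing about the split, because the composite pools two visits and planning values can be wrong. It is a reason to report the split.

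**The case against.** The strongest reply is that the check does contain a laboratory test in every reported period, and that a recalled diagnosis is not a second report of CAS. CAS comes from an interview, and the diagnosis probably comes from a separate computer survey item. The plan states the composite openly and calls it a bacterial STI diagnosis; only the shared heading speaks of biomarkers. The self-report limb also has a purpose, since it picks up infections diagnosed and treated between laboratory visits. All of this stands. It limits the point to labelling and missing detail, but it does not supply the missing split. The supplemental material may give it, but that is not among the documents available here.

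Four stronger readings are tempting, and the documents do not support them.

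- *The corroboration is not biological at all.* The first limb of the definition is a laboratory result, so this is wrong.
- *The contrasts could arise with no laboratory difference.* This is arithmetically possible but strained. Assume a common laboratory rate of 7% at baseline, independent of self-report. Self-reported diagnoses would then have to be 1 − 0.695/0.93 = 25.3% against 1 − 0.923/0.93 = 0.8%. The premise of equal laboratory rates is assumed, not shown.
- *The check should use the analysed TRB variable, which is set to 0 under the PrEP rule.* That rule concerns HIV risk. The documents claim no PrEP protection against gonorrhea or chlamydia, so casual CAS as reported is the right comparator.
- *STI among men denying casual CAS shows under-reporting.* Eligibility also admits CAS with a non-monogamous or serodiscordant main partner, so such infections need not come from casual sex. A laboratory-only check would not settle this either.

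**Conclusion.** The point holds in a limited form. The STI indicator combines laboratory and self-reported diagnoses, is presented as a biomarker check, and is reported only as a composite. The check is not purely biological, its biological share cannot be seen, and shared disclosure tendencies could inflate the agreement.

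The size of any inflation is unknown. Under the least favourable allocation, the 3/6-month contrast disappears at a self-report-only share of about 46% among positive CAS reporters; the other two need about 75%. If the share is the same in both groups, the association survives even at 75%. These bounds rest on assumed shares and on the period-by-period reading of the indicator.

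The consequence is confined to the supporting validity evidence for a self-reported outcome. The TRB variable comes from the follow-back interview, and the STI composite enters neither that variable nor the growth models described. The stated power does not change. The revision is worth making because it is cheap and determines what the corroboration statement can support.

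**What to change.** In the corroboration section:

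1. Make laboratory-confirmed rectal or urethral positivity at baseline, 6 and 12 months the biomarker check. Tabulate it by casual CAS self-reported at the same visit and by arm, with numerators and denominators.
2. Show self-report-only diagnoses in a separate row.
3. Keep the composite as a supplementary row, labelled as laboratory or self-reported diagnosis, so that infections found between laboratory visits are not lost.
4. Base the corroboration statement, here and under Primary outcomes, on the laboratory-only contrast, and qualify it if that contrast does not support it.

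The cost is recoding data already held and one further table. The laboratory rows will have fewer positives and less precision, more so when split by arm, and there will be no biomarker check at 3 and 9 months, where no specimen is scheduled. The text should say so.

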Participants are considered enrolled in the study when they have completed informed consent. Randomization occurs immediately after the baseline appointment.

Informed Consent Process

Details of the study are reviewed with the prospective study participant by a research assistant who is trained and cleared to conduct assessments and is knowledgeable about the research study. This discussion is a critical component of the consent process and the prospective study participant will be given adequate time for this discussion and to read the written consent form. The research assistant is available to answer questions about the study including participant responsibilities, benefits, risks, and alternatives. The participant reviews the consent form and it is signed and dated by both the participant and study staff member conducting the assessment. A copy of the signed consent form will be given to the participant and the original will be kept securely by the project coordinator separate from other assessment materials.

Post-COVID: Participants review written consent information prior to their baseline appointment. The baseline survey link directs participants to a landing page containing detailed consent information. At the beginning of the baseline assessment, study staff provides an oral review of consent information and confirms age eligibility via Zoom. After reviewing this information, participants are asked to affirm their consent/assent to participate. A copy of the electronic consent form is emailed to the participant upon request.

Randomization Process/Systems

Participants are randomized at the end of their baseline assessment into one of two intervention conditions: 1) delivery of the 4 session PARTNER intervention or 2)

delivery of 4 education sessions. Each participant's condition is tracked in the access tracking database maintained by the project manager.

The study employs a stratified block randomization procedure with equate study conditions based upon 1) age discrepancy between partners, 2) relationship length, and 3) race and ethnicity using Qualtrics.

Schedule of Assessments

Sessions occurs approximately once per week for three weeks beginning one week after completion of the baseline assessment and session 1. There is a 12 week window for intervention completion, i.e. all four sessions must be completed within 12 weeks of the baseline assessment.

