Several considerations led to the inclusion of model covariates. Consistent with guidance for the analysis of data from randomized controlled trials that utilize stratified randomization (16), stratification variables were included as covariates in regressions predicting latent growth factors. The COVID-19 pandemic and recovery corresponded with changes in substance use and sexual behavior among SMM. To account for this, models incorporated a dichotomous, timevarying predictor indicating whether an assessment occurred before or after March 2020. All models were calculated using full-information maximum likelihood estimation in Mplus Version 8.0. This permitted the retention of all randomized cases consistent with the intent-to-treat paradigm. Model significance was evaluated using a robust log-likelihood $\chi 2$ test comparing the log-likelihood of the specified model to a null-model – in which all structural coefficients associated with the regression of latent growth factors on condition and site were constrained to be zero. Where model results were significant, the effect of the PARTNER intervention was evaluated by examination of regression parameters for Slopes 1 and 2. Given the directional nature of hypotheses, single-sided p-values were used to determine the

significance of the intervention effect. When evaluating the significance of putative moderators and associated interaction terms, two-sided p-values were used.

Power analyses

We utilized the *Test for the Ratio of Two Negative Binomial Rates* module in PASS 19 to evaluate power to detect between-condition differences in drug use frequency at any one follow-up time point. Power (1-beta) was set to .80 and the probability of type II error (alpha) was set to .05. The number of exposures was set to 30 (the number of days of use assessed in the TLFB). The rate of use in the education condition was set to 3, 6, and 9. Meanwhile dispersion values of 1, 2, and 4 were tested. Power was highest at low levels of dispersion and high based rates of use in the education condition. Under these circumstances, the study has power=.80 to detect a rate ratio of 0.70 or a 30% reduction in drug use instances. At high levels of dispersion and low base rates, the study would be expected to detect a rate ratio of 0.48.

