We will strive to ensure that randomization will not produce any significant differences in participant characteristics that require control in subsequent longitudinal analyses. Baseline cross-site variance in participant characteristics will be assessed using standard tests of mean differences for both biological markers and self-reported measures of substance use, TRB, and PrEP uptake/adherence. Assignment differences in baseline demographics will be assessed using standard non-parametric measures of association. Any observed differences will be controlled for in subsequent models.

IMPLICATIONS AND LIMITATIONS

Policy/Methodological Implications

This application has focused implications for the_biomedical prevention of HIV in a highly vulnerable population as well as broad methodological implications for PrEP research. The proposed project tests an intervention which addresses PrEP uptake in a high-priority population for whom no existing interventions are tailored (partnered SMM meeting CDC criteria for PrEP candidacy). It therefore addresses PrEP uptake and adherence (critical steps in the cascade) for an under-served and highly vulnerable population. Furthermore, the secondary aims of this proposal include the validation of fingernail assays to assess PrEP adherence. This innovation has broad implications for the study of PrEP.

Primary limitations

1) The absence of data from relationship partners. The use of individual (rather than dyadic) intervention is intended to enhance scalability. Participants will report relationship functioning as well as their perception of their partners' drug use, sexual behavior, PrEP uptake (see APPENDIX B; Partner health behavior survey). This will provide proxy data which can inform future studies. 2) Limited data on the efficacy of the PARTNER intervention. We have completed all aspects of intervention development and established the acceptability/feasibility of PARTNER. The need for pilot efficacy data is reduced by the fact that PARTNER incorporates all aspects of YMHP, which has demonstrated efficacy¹⁶, and the use of a control condition which has been employed in previous NIH funded trials¹⁶. 3) Recruiting partnered SMM. A strong infrastructure exists to support recruitment efforts. We have developed recruitment

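### On its natural reading, the growth model lets condition predict the baseline intercept, which costs precision on Slope 1 and adds a needless parameter to the overall test

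*Combined protocol and SAP*

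**What the plan says.** The Detailed analytic plan (under Quantitative Analysis Plan) describes a piecewise latent growth model with two slopes: one from baseline to 3 months, and one over the later follow-up. On treatment it says that "Model 1 included the main effect of treatment on growth factors". The overall test compares the fitted model with a null model in which "all structural coefficients associated with the regression of latent growth factors on condition and site were constrained to be zero". Only when that test is significant is the treatment effect read, and then "the effect of the PARTNER intervention was evaluated by examination of regression parameters for Slopes 1 and 2", with one-sided p-values.

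On adjustment, "stratification variables were included as covariates in regressions predicting latent growth factors", and "models incorporated a dichotomous, timevarying predictor indicating whether an assessment occurred before or after March 2020". The baseline outcome is not in this list. The text never mentions the intercept. It neither fixes the effect of condition on baseline at zero nor regresses the slopes on the baseline level.

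Two other sections bear on the point. Under Randomization Process/Systems, "Participants are randomized at the end of their baseline assessment into one of two intervention conditions". Under Equivalency Checks, "Any observed differences will be controlled for in subsequent models".

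**The concern.** A piecewise model of this kind has three growth factors: an intercept (baseline), Slope 1 and Slope 2. The null model refers to the growth factors as a group, and the text narrows to the two slopes only when it comes to reading the treatment effect. The natural reading is therefore that condition predicts all three.

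Baseline is measured before randomisation, so the condition effect on the intercept is zero by design. If the path is left free, the model fits whatever chance difference appears at baseline and measures Slope 1 from there. Baseline then enters the Slope 1 contrast with a weight of 1 rather than its regression weight, and chance imbalance is carried into the estimate.

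The plan itself expects the largest response in the first interval, so Slope 1 is where precision matters most. The overall test acts as a filter before either slope is read, and a parameter that is zero by design lowers the chance of passing it.

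**Working it through.** **1. The plan's own power figure.** Inputs from the abstract and Power analyses: 240 participants with equal allocation (120 per arm), power .80, alpha .05, 30 exposures, control rates 3 to 9, dispersion k of 1 to 4. For a ratio of two negative binomial rates,

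n per arm = (z_α + z_β)² × [1/(t·r0) + 1/(t·r0·RR) + 2k] / (ln RR)².

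- Best case (r0 = 9, k = 1), two-sided: 7.849 × [1/270 + 1/(270 × .696) + 2] / (ln .696)² ≈ 120, so RR = 0.696 (plan: 0.70).
- Worst case (r0 = 3, k = 4): 7.849 × [1/90 + 1/(90 × .484) + 8] / (ln .484)² ≈ 120, so RR = 0.484 (plan: 0.48).

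A one-sided test with 96 per arm (80% retention) fits about as well (0.698 and 0.487). The figures reproduce, but they concern a difference at one follow-up. The plan gives no power for Slope 1, so the size of the loss needs assumptions.

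**2. Two waves, linear scale, unit variance, correlation ρ.** The change-score contrast has variance proportional to 2(1 − ρ), and the baseline-adjusted contrast 1 − ρ². Their ratio is (1 + ρ)/2, which is .625, .75 and .875 at ρ = .25, .50 and .75. A simulation (120 per arm, 5,000 runs) gave .625, .748 and .883, and both estimators were unbiased.

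**3. Five waves (0, 3, 6, 9, 12 months), piecewise model, complete data.** Slope 2 lets the later waves inform the 3-month level. A line through four equally spaced follow-ups estimates its first point with residual variance factor 1/4 + 1.5²/5 = 0.70. Under exchangeable correlation:

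- intercept path free: 1 + ρ + 0.7(1 − ρ) − 2ρ = 1.7(1 − ρ);
- intercept path fixed at 0: ρ + 0.7(1 − ρ) − ρ² = (1 − ρ)(0.7 + ρ);
- ratio: (0.7 + ρ)/1.7.

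The AR(1) values come from the same generalised least squares calculation done numerically. The ρ range is the one the plan states for STI and PrEP uptake, and it is assumed here for all outcomes.

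| ρ | Ratio, exchangeable | Variance cut | Ratio, AR(1) | Variance cut |
|---|---|---|---|---|
| .25 | .95/1.7 = .559 | 44% | .562 | 44% |
| .50 | 1.20/1.7 = .706 | 29% | .725 | 28% |
| .75 | 1.45/1.7 = .853 | 15% | .872 | 13% |

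For equal Slope 1 precision under exchangeability, the free-path model needs 1/ratio − 1 = 79%, 42% and 17% more participants. Slope 2 variance is unchanged under exchangeability and falls by 3%, 11% and 16% under AR(1).

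**4. Power for Slope 1, one-sided .05 as planned.** If the free-path test has power .80, the constrained test has Φ(2.486/√ratio − 1.645). Under exchangeability this is .95, .91 and .85 at ρ = .25, .50 and .75.

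**5. Count scale.** One simulation of Poisson-lognormal counts capped at 30, with very stable individuals, gave a variance ratio of .886, an 11% cut. Power goes from .80 to Φ(2.486/√.886 − 1.645) = .84. No binary outcome was simulated.

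**6. Overall test at .05 (non-central χ²).**

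- Condition paths only: the non-centrality giving .80 on 2 df is 9.63. The same value on 3 df gives .744.
- One site contrast on all three factors kept in: .80 on 5 df needs 12.83. On 6 df this gives .771.

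**The case against.** The strongest objection is that the free path is inferred. The intercept is not named, the treatment effect is read from the two slopes only, and the plan follows a cited published procedure for piecewise growth models that may settle the specification but cannot be consulted here. This stands as a limit on certainty. It does not remove the point, because the plan still has to say how baseline enters its primary model.

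A reader might go further and call Slope 1 an unadjusted, raw change score that discards baseline. The documents do not support that. The growth factors are adjusted for the stratification variables, the models carry a COVID-period predictor, and later waves inform the 3-month level. Baseline is used, with a less than optimal weight.

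The Equivalency Checks section could be offered as the missing adjustment. It acts only on differences that are observed, and its check of the outcome measures is framed across sites. The Detailed analytic plan does compare baseline outcomes between conditions. Neither is the same as a pre-specified adjustment applied whatever the data show.

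Finally, the linear figures describe a scale the primary outcomes do not have, and the documents give no correlation for the drug-use or sexual-risk counts. This also stands. It is why the count result is reported beside the linear range.

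**Conclusion.** On the natural reading, the plan spends a parameter on a baseline difference that randomisation makes zero, and so estimates Slope 1 less precisely than its data allow. A reader might infer that the Slope 1 estimate is biased or its test invalid. Neither follows: under randomisation the estimator is unbiased, and a free intercept is a valid, less efficient choice.

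Fixing the path would cut Slope 1 variance by about 44% to 15% under exchangeable correlation (44% to 13% under AR(1)). This assumes a linear scale, complete data and ρ from .25 to .75. For the actual count and binary outcomes the gain will differ and may be smaller; the single count result is 11%. The gain in the overall test is from .744 or .771 to .80, depending on whether site terms stay in it. The plan does not say how many site terms there are.

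**What to change.** In the Detailed analytic plan, state that condition predicts Slopes 1 and 2 only and that the condition-to-intercept path is fixed at 0. Keep the stratification covariates on the intercept. Drop the condition-to-intercept parameter from the overall test, and list the paths that remain in it, including any site terms.

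The cost is one constraint in the Mplus code and one sentence per model. No new data are needed, and nothing is assumed beyond randomisation. The plan is written largely in the past tense, so the models may already have been run. If so, report the constrained model openly as an added analysis beside the one already fitted.
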